1. PREVIOUS STUDY HISTORY

Has this study ever been reviewed and rejected/disapproved by another IRB prior to submission to this IRB?

☒ No ☐ Yes – if yes, please explain: []

2. BRIEF SUMMARY OF RESEARCH

- *The summary should be written in language intelligible to a moderately educated, non-scientific layperson.*
- *It should contain a clear statement of the rationale and hypothesis of your study, a concise description of the methodology, with an emphasis on what will happen to the subjects, and a discussion of the results.*
- *This section should be ½ page*

Treatment for certain types of bladder cancer (BC) involves the removal of the bladder and construction of a new voiding system and is physically and psychologically profoundly challenging for patients and caregivers. Based on our published literature and extensive pilot data, patients and caregivers have extensive unmet informational, social, psychological, instrumental, and medical needs from the time of diagnosis, through treatment and recovery which are not adequately addressed by health care professionals.

We propose to address these unmet needs through the refinement and evaluation of a comprehensive, 2-part (in-person and web-based) intervention, geared towards the patient and caregiver. Specifically, during Aim 1, the formative phase, we propose to further refine our newly developed intervention components with the help of an established patient/caregiver advisory board. The intervention, Recovery Support for Bladder Cancer (RSBC), consists of a pre-treatment, in-person preparatory instructional session with a trained health care professional (Module 1) to equip patients and caregivers with the skills to adjust to the upcoming treatment and recovery period. This is followed by a post-treatment, interactive web-based program (Module 2) to provide further support for both patients and caregivers to enhance quality of life (QOL) and reduce infections and nurse/ER visits. The RSBC intervention will be evaluated in a 12-month randomized controlled trial (Aim 2) among patients and caregivers (N=287 participants; 238 final sample) against a time and attention comparison condition that incorporates modules focusing on wellness. Primary outcomes for both patients and caregivers will be improved QOL, which is hypothesized to be significantly higher among participants randomized into RSBC. Secondary outcomes will be fewer infections and nurse-ER visits for patients randomized into RSBC. Aim 3 proposes moderator (i.e., age, gender, surgical diversion type) and mediator (i.e., patient activation, distress) analyses of intervention efficacy. We hypothesize that RSBC will be significantly more successful among (a) older, (b) female participants, and (c) patients with a conduit diversion type. Elevated levels of patient activation (i.e., higher self-care knowledge, self-efficacy, lower distress) will mediate the intervention effects. Exploratory Aim 4 will examine the costs and potential savings

associated with developing and implementing the RSBC intervention. We hypothesize that initial development and implementation costs of RSBC will be offset by reduced nurse/ER visits.

The scientific premise is strong and supported by an established theoretical framework, extensive pilot data and a rigorous application of clinical research methods. The proposed study is highly innovative, as it comprehensively addresses unmet needs of both patients and caregivers from pre- and (immediate) post-treatment to recovery. This is achieved through an innovative combination of in-person preparation and skill-building and web-based technology. If successful, RSBC has the potential to significantly change clinical care for patients and caregivers with BC.

3. INTRODUCTION/BACKGROUND MATERIAL/PRELIMINARY STUDIES AND SIGNIFICANCE

- *Describe and provide the results of previous work by yourself or others, including animal studies, laboratory studies, pilot studies, pre-clinical and/or clinical studies involving the compound or device to be studied.*
- *Include information as to why you are conducting the study and how the study differs from what has been previously researched, including what the knowledge gaps are.*
- *Describe the importance of the knowledge expected to result*

More than 70,000 Americans will be diagnosed with bladder cancer (BC) in 2017, leading to more than 16,000 deaths. BC is most likely to develop in older, White men and individuals with a history of smoking.¹ Because BC tumors are asymptomatic in the beginning stages of development, diagnosis is usually delayed until more advanced stages of the disease have developed. Standard of care for muscle invasive bladder cancer (MIBC) and certain cases of non-muscle invasive bladder cancer (NMIBC), involves the surgical removal of the bladder with or without neoadjuvant chemotherapy. As part of the bladder removal, the surgical team constructs a new diversion method and urinary reservoir. Depending on clinical factors and patient preferences, there are three possible urinary diversion methods: (a) ileal conduit, which involves the construction of a stoma from intestinal tissue and the placement of an external bag to hold urine; (b) Indiana pouch, which involves the construction of a stoma and internal reservoir from intestinal tissue that is emptied through self-catheterization; and (c) neobladder, in which an artificial bladder is fashioned from intestinal tissue. A majority of patients experience significantly elevated rates of depression and anxiety and significant declines in quality of life (QOL) following treatment.^{2,3} QOL is generally compromised with patients reporting significant declines in the areas of physical, social, and emotional well-being.^{4,5} Elevated levels of psychological distress (i.e., anxiety, depression) have been reported by as many as 70% of survivors and have been associated with frequent urinary incontinence as well as leakage, odors, and difficulties with standard activities of daily living (e.g., sleeping, dressing, socializing, traveling). Inconvenient stoma location and ineffectual self-care (e.g., care for one's stoma, in-ability to self-catheterize or empty one's neobladder) have

also been associated with elevated distress and severely compromised QOL.^{6,7} Throughout the treatment and recovery period, patients and caregivers need to be involved in crucial aspects of patient care.⁸⁻¹⁰ For example, prior to surgery, patients need to be consulted on optimal stoma placement by a stoma nurse and be informed about the surgical procedure and the immediate post-surgical recovery demands. Post-surgery, patients will need to learn how to live with an artificial exit, and the use and care of stoma appliances. Caregivers play a crucial role in supporting the patients in these self-care tasks.¹¹ In addition, patients who receive a neobladder need to learn to void with the Valsalva maneuver—a skill that is not mastered by every patient. Patients that do not master the Valsalva maneuver need to learn to self-catheterize to empty the bladder. Patients with a neobladder also frequently encounter nightly episodes of incontinence, thus further impacting patients and caregivers. Virtually all bladder cancer survivors and their caregivers need to cope with the prospect of a slow recovery, a diminished social life, reduced mobility, a changed body image and fears of recurrence.^{4,5,12,13} Yet, few studies have addressed the needs of this underserved cancer population.

The literature suggests that family caregivers face a variety of burdens and unmet needs along each stage of the patient's treatment. Specifically, caregivers face burdens regarding access to care services and knowing when to contact the care team, dealing with emotional and psychological stress, managing normal daily activities (e.g., finances), communicating with the patient, knowledge on caregiver roles and illness expectations, and maintaining spirituality (e.g., hope for the future).¹⁴ In addition, post-surgery care service visits (e.g., rehabilitation, visiting nurse appointments) are often coordinated by the caregiver.¹³ Psychologically, caregivers must manage their own emotional distress often buffering their feelings as not to upset the patient. The unmet emotional caregiver burden is a strong predictor of poor mental health across all phases of survivorship.¹⁵ Many caregivers face significant disruptions to their daily life when caring for their loved one. The majority of caregivers spend an average of 21 hours per week caring for the patient, which is the equivalent of adding a half-time job to their schedule.¹⁶ Post-treatment training and education for BC caregivers is nonexistent, which means that post-operative care techniques are often learned by trial and error. The literature suggests that a caregiver-targeted intervention to provide support and education is essential to minimize caregiver burden and ultimately maximize patient QOL.¹⁶⁻¹⁸ The goal of the proposed research is to fill this void in the literature by addressing the biopsychosocial consequences of BC surgical treatment in a patient- and caregiver-centered approach through the careful preparation of patients and their caregivers before treatment, as well as through post-treatment support. Our prior work (see D.2.)^{4,13} has demonstrated that lack of time and hospital staffing constraints lead to less than optimal patient preparation. Pre-operative visits, conducted by the surgical staff, mainly focus on the upcoming surgical procedure, with less attention given to the complex psychosocial demands of recovery. Ideally, pre-operative care includes instruction from a stoma nurse to discuss stoma placement with patients based on their body type, clothing, and lifestyle preferences. However, this pre-operative counseling is not regularly performed, leaving the surgeon to make the decision about stoma placement without patient

input.¹⁹ Furthermore, crucial post-operative recovery and management information is given to the patient shortly before discharge, a time when information processing is compromised by multiple discharge tasks, lack of privacy, and pain medication. Despite caregivers' crucial role in patient recovery, they are typically not included during discharge instructions.^{4,13}

In addition, preparation mainly focuses on post-treatment-related medical issues and the clinical mechanics of recovery, paying less attention to the psychosocial aspects of BC and recovery. Finally, information processing is impacted by patient psychological and emotional factors (e.g., concerns and worries about fatigue, pain, future QOL), undermining the understanding and execution of necessary health promotion tasks, as suggested by the literature²⁰ and our prior work (see D.2.). Our pilot data^{4,13} demonstrate the important role caregivers play in the recovery of patients, thus it is crucial that caregivers are included in all patient-directed communications and educational processes. In sum, the inclusion of caregivers in the provision of survivorship-related techniques and information is essential and should be accomplished prior to surgery treatment.

In the current application we are using two modes of information delivery: (a) a pre-treatment preparatory module (Module 1) conducted by a trained health care provider that focuses on preparing for post-surgical tasks and (b) a post-treatment web-based education and support program (Module 2) that provides information and support for patients and caregivers in the post-treatment phase. Our own research has shown that family caregivers provided a large majority of stoma support^{30,31}. However, caregivers are often unprepared for this role, leading to increased patient complications as well as patient and caregiver distress. Routinely, patients are referred to a visiting nurse service to provide basic medical support during the immediate post-operative period. Our research found inconsistent and uneven support for bladder cancer patients after receiving a cystectomy, and no support for caregivers. Overall, patients perceive the support from visiting nurses as suboptimal; nurses lack sufficient knowledge of bladder cancer and its stoma appliances and were largely unavailable because of busy schedules. Thus, there is a clear need for timely on-demand information and support addressing critical areas of recovery (e.g., medical, psychosocial) at the convenience of the patient and their caregiver. Our combined in-person and web-based program, focusing on the patient and the caregiver, addresses this significant unmet need of this underserved population. Americans have become accustomed to receiving health information from the Internet. Most Internet users (72%) have looked online for health information within the past year.²¹ Though many websites provide health information, such information is often inaccurate, sensational [e.g., “ten tips to improve (insert health problem here)”], and not tailored or targeted to specific conditions or populations. Yet, there are many advantages to developing and providing web-based solutions: (a) patients can consume the information at their own schedule, in a private place, and as often as they desire; (b) information sharing with caregivers; (c) information can be transmitted through multiple channels (personal computer, tablet, or phone); (d) content can be augmented through videos, graphics, testimonials, and interactive activities; (e) content can be

tailored to specific time-points in the recovery trajectory, treatment approaches, and targeted to specific groups; (f) access transcends geographical barriers; (g) patient recovery progress and trajectory can be tracked in real-time, allowing for immediate feedback. Overall, web-based patient education has been shown to be effective in increasing disease-related knowledge and improving health behaviors and self-management skills.²²⁻²⁹ Based on that data and our experience in developing web-based software tools for health education (see D.2.d), we will augment our in-person instructions and preparations delivered in Module 1 with a web-based program in Module 2 and optimized for tablet delivery that will be available to patients and caregivers who are randomized to the intervention group. Patients and caregivers in the control group will receive the “Facing Forward” brochure from the National Cancer Institute as part of Module 2. This time and attention comparison module will be provided to subjects in a printed or electronic format. There are 2 versions of the brochure- one for patients and one for caregivers. The proposed application has a strong scientific premise in that the study will comprehensively address the identified gaps through a novel intervention for both patients and caregivers. Significant gaps in supportive care persist in the treatment of patients diagnosed with MIBC.^{30,31} These gaps include: (a) insufficient pre-treatment patient preparation and information from physicians and nursing staff and insufficient psychosocial support; (b) inadequate post-treatment discharge instructions and skills building for post-treatment recovery; (c) insufficient support for caregivers, leaving caregivers with inadequate skills and psychosocial support; and (d) lack of interventions targeting MIBC patients and caregivers. The premise is further strengthened through our preliminary data demonstrating the synergistic effects of in-person support (see D.2.c.) combined with on-demand web-based information and support (see D.2.d), as well as an established literature on web-based supportive interventions, for cancer patients and caregivers.^{25-27,29}

4. OBJECTIVE(S)/SPECIFIC AIMS AND HYPOTHESES

- *A concise statement of the goal(s) of the current study.*
- *The rationale for and specific objectives of the study.*
- *The goals and the hypothesis to be tested should be stated.*

[Bladder cancer (BC) is a severe but psychosocially unaddressed disease that involves highly invasive surgical procedures. Most commonly, patients undergo the surgical removal of the bladder, prostate, and infected lymph nodes, followed by the construction of a new voiding system [i.e., either an ileal conduit (a stoma with external bag), stoma with internal reservoir, or neobladder]. The treatment and recovery period is physically and psychologically extremely challenging for patients and their spouse/partners (henceforth defined as caregivers). Based on our published literature and pilot data, patients and caregivers have persistent and dramatic unmet needs from the time of diagnosis, through treatment and during recovery. These needs in the areas of informational, social, psychological, instrumental, and medical domains are not adequately addressed by health professionals. Specifically, within the medical domain patients have to cope with a

lengthy surgical intervention, significant clinical complications, high re-hospitalization rates, and a long recovery period. Lack of adequate support and self-care information contribute to a difficult post treatment adjustment period. Psychosocial distress is fueled by concerns over an altered body image, feelings of isolation through restrictions in social activities and fears of recurrence (reflected by a ~46-57% 5-year recurrence rate). Caregivers have to learn and adjust to sensitive and potentially difficult caregiving tasks, such as stoma care. Not surprisingly, the complex care regimens and high recurrence rates are associated with high levels of distress among patients and caregivers. The scientific premise of this application is based on a strong conceptual model, data analyses from our previously developed survivorship interventions and our pilot studies, which include extensive qualitative assessments of unmet needs of BC patients and caregivers, and development and testing of intervention components. Our pilot work point to the necessity for support across the disease and recovery spectrum. In particular, we have identified three understudied needs that require novel interventions to better support patients and caregivers: (1) pre-treatment preparation, (2) post-treatment/discharge self-care challenges, and (3) long-term adjustment. To address these needs, we will refine and evaluate a comprehensive, synergistic in-person (Module 1) and web-based program (Module 2) geared to the patient and caregiver [*Recovery Support for Bladder Cancer* (RSBC)]. The **overall purpose** of the proposed project is to improve patient and caregiver quality of life (QOL), reduce infections and nurse/ER visits, and reduce costs by enhancing self-care knowledge and self-efficacy.

Specific Aim 1 (Formative work): To further refine our newly designed intervention components for patients with BC and caregivers. Our prior work suggests an in-person preparatory visit before treatment combined with a post-treatment web-based intervention targeting patients and caregivers. The components will be further refined through usability testing with the involvement of our patient/caregiver and physician advisory board.

Specific Aim 2: Conduct a rigorous 12-month randomized controlled trial with BC patients and their caregivers at three diverse hospital systems. Patient and caregivers (N=287 participants) will be randomized into the (a) RSBC intervention or (b) time and attention comparison condition that incorporates appropriate health promotion adapted from our prior work (final N= 238 participants). Patients and caregivers in the intervention group compared to the comparison group will experience improved QOL (**primary outcome**) both in the short- (6 mo post-op) and long-term (12 mo post-op; H1), and will experience fewer infections and nurse/ER visits (patients only, **secondary outcomes**; H2).

Specific Aim 3: Conduct moderator and mediator analyses. 3a: To examine the impact of identified moderators on intervention efficacy. Older age, female gender, and type of surgical diversion (i.e., non-neobladder) will moderate the relationship between the intervention and QOL (H3). **3b:** To examine the impact of identified

mediators on intervention efficacy. Higher levels of patient activation (i.e., self-care knowledge, self-efficacy) and lower levels of distress will mediate the intervention effect (H4).

Exploratory Aim 4: To examine the costs and potential savings associated with developing and implementing the RSBC intervention. Costs will be recorded in three categories: development, implementation, and maintenance of intervention. Potential savings will be recorded regarding emergency room care and unplanned visiting nurse home visits. Over time, the savings from the reduced ER/Nurse visits will surpass the costs of the intervention (H5) and the intervention will be cost effective (H6).

5. RESOURCES AVAILABLE TO CONDUCT THE HUMAN RESEARCH

- *Explain the feasibility of meeting recruitment goals of this project and demonstrate a potential for recruiting the required number of suitable subjects within the agreed recruitment period*
 - *How many potential subjects do you have access to?*
- *Describe your process to ensure that all persons assisting with the trial are adequately informed about the protocol and their trial related duties and functions*

Advisory Board & Usability Testing (Aim 1): Recruitment goals for this phase of the study are feasible in that this patient recruitment will be completed through the assistance of Drs. [name] and [name] who work directly with this population and can provide use with referrals of patients who express interest in participating in this phase. Recruitment will involve 6 patient and caregiver pairs who have agreed to serve as a part of our advisory board. Additionally we can base recruitment feasibility off of the data presented below for the RCT.

RCT (Aim 2): Patient availability was reassessed in June 2020 due to the impact of the COVID-19 pandemic. We anticipate 480 participants to be available during the recruitment period (2020-2023) between both study sites. Based on our pilot data, 90% of patients have a caregiver. Given our extensive experience working with cancer patients, we assume, that 70% of patients will agree to participate in the proposed study and 70% of patients will remain in the study at 12 months (i.e., we are projecting a 15% attrition rate). The 70% acceptance rate has been confirmed by a pilot survey of recent bladder cancer patients across all sites. Therefore, we anticipate enrolling 287 participants over three years. This should yield a final sample of 238 participants. Based on these numbers we expect to enroll a total of 97 participants at NWH. Participating physicians and staff at the Arthur Smith Institute for Urology, and Staten Island University Hospital, will be informed and trained in the procedures of this protocol. PI, [name] will advise staff of their duties and functions of this study.

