8. NUMBER OF SUBJECTS

- *Indicate the total number of subjects to be accrued locally. If applicable, distinguish between the number of subjects who are expected to be pre-screened, enrolled (consent obtained), randomized and complete the research procedures.*
- *If your study includes different cohorts, include the total number of subjects in each cohort.*
- *If this is multisite study, include total number of subjects across all sites.*

Advisory Board and Usability Testing (Aim 1):
Patient and Caregiver Pairs $n=6$ NWH / $n=6$ FCCC/Temple
12 Pairs Total

RCT (Aim 2):

Total	N=238 (N=287 + 15% attrition) 
 • Patients=153, Caregivers=85
NWH	N=78 (N=97 + 15% attrition)
FFCC	N=141 (N=190 + 15% attrition)

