9. STUDY TIMELINES

- *Describe the duration of an individuals participation in the study*
- *Describe the duration anticipated to enroll all study subjects*
- *The estimated date of study completion*

Advisory Board and Usability Testing (Aim 1): The advisory board members will speak over the phone with the study team once in Year 1 for approximately 20 minutes to discuss RSBC intervention. At the end of phone call, CRC/RA will ask participants if they would be interested in the usability testing. Individuals participating in the usability testing will be enrolled into the study for 1 day for approximately 60 minutes per pair.

RCT (Aim 2): An individual's participation in this phase is expected to last for 12 months. To better understand participant satisfaction and use of the RSBC intervention program (CRIS), they may be invited for a brief follow-up interview.

Duration to Enroll: Duration of enrollment is expected to last 2.5 years, from the 1st enrollment of individuals for the advisory board to the final enrollment of individuals for the RCT phase.

Date of Study Completion: We anticipate study completion by December 2024.

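### The sample-size figures in sections 5 and 8 are mutually inconsistent, and no single retention rate reproduces them

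*Combined protocol and SAP*

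**What the plan says.** - Section 5 projects that "70% of patients will remain in the study at 12 months (i.e., we are projecting a 15% attrition rate". The 70% is stated for patients. The section then gives 287 enrolled, a final sample of 238, and 97 enrolled at NWH.
- Section 8 repeats the total as "N=238 (N=287 + 15% attrition" and splits the final number as "Patients=153, Caregivers=85".
- Section 8 gives the site rows as "N=78 (N=97 + 15% attrition" for NWH and "N=141 (N=190 + 15% attrition" for the second site (FFCC in that table).
- Sections 2 and 4 repeat 287 and 238.
- Section 12 plans separate analyses of patients and caregivers with a linear mixed model. It contains no power calculation: it gives no power, effect size or standard deviation for sizing the trial.
- Upstream of these figures, section 5 says "We anticipate 480 participants to be available during the recruitment period (2020-2023) between both study sites" and "Therefore, we anticipate enrolling 287 participants over three years". Section 9 says "Duration of enrollment is expected to last 2.5 years", counted from the first advisory-board enrolment.

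**The concern.** A 70% retention rate and a 15% attrition rate cannot both describe the same follow-up, yet section 5 offers one as a restatement of the other. In section 8 the 15% label is attached to three rows whose implied losses all differ, and the site finals do not add to the total. Because section 12 has no power calculation, these are the only figures from which a reader can judge how many patients and caregivers will be available at 12 months, one of the two time points named in the primary hypothesis (section 4). If they disagree, the expected size of each separately analysed group is unclear.

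**Working it through.** **Inputs.** Enrolled 287, final 238, retention 70%, attrition 15% (section 5); patients 153, caregivers 85, NWH 97 to 78, FFCC 190 to 141 (section 8).

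**Formula.** Final = enrolled × (1 − attrition).

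**Total**
- At 15%: 287 × 0.85 = 243.95, about 244. The stated 238 is 6 lower (6/244 = 2.5%).
- At 30%: 287 × 0.70 = 200.9, about 201, if the rate applies to all participants. The stated 238 is 37 higher.
- Implied by the plan: 1 − 238/287 = 17.1%.

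**Site rows**

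| Site | Enrolled | Stated final | Implied attrition | At 15% | At 30% |
|---|---|---|---|---|---|
| NWH | 97 | 78 | 1 − 78/97 = 19.6% | 82.45 | 67.9 |
| FFCC | 190 | 141 | 1 − 141/190 = 25.8% | 161.5 | 133 |
| Sum | 287 | 219 | 23.7% | 244 | 201 |

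Neither rate gives either stated site final.

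**Sums.** 97 + 190 = 287 agrees with the total enrolled. 153 + 85 = 238 agrees with the total final. 78 + 141 = 219 is 19 short of 238.

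**Possible source of the 141.** 238 − 97 = 141 exactly, which suggests that NWH's enrolled number was subtracted where its final number was meant. Using the final number, 238 − 78 = 160, and 1 − 160/190 = 15.8%. This is an inference; the documents do not say how 141 was obtained.

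**Group sizes, keeping the 153:85 split** (153/238 = 0.643)
- From 244: about 157 patients and 87 caregivers.
- From 201: about 129 patients and 72 caregivers.

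**Illustrative detectable difference.** The plan states none of the assumptions used here: 80% power, two-sided 0.05, equal arms, one comparison, no covariates. With n the total in both arms, d = 2 × (1.96 + 0.8416)/√n.

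| Basis | Patients: n, d (SD) | Caregivers: n, d (SD) |
|---|---|---|
| As stated | 153, 0.45 | 85, 0.61 |
| 15% attrition | 157, 0.45 | 87, 0.60 |
| 70% retention, both groups | 129, 0.49 | 72, 0.66 |

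**The case against.** The best defence is that 15% is the intended rate and 70% is a slip. The 70% retention figure appears once, directly after a 70% acceptance rate, whereas 15% appears in the same sentence and in all three rows of section 8. On that reading 238 is within 2.5% of the computed 244 and on the cautious side, 141 is probably one bad cell, and the detectable differences hardly move. Also, a mixed model can use participants with partial follow-up, so completers are not the only source of information. All of this is fair, and it limits the consequence. It does not remove the contradiction in section 5, and it does not explain NWH, where 97 to 78 is 19.6% under a 15% label.

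A reader might go further and infer that 238 is simply wrong, or that every size figure in the plan is. The documents do not support that: the site enrolments add to 287, the patient/caregiver split adds to 238, and 238 is slightly conservative at 15%. Three other observations are tempting as proof and fall short of it:
- 153/0.85 = 180 and 85/0.85 = 100, which would fit an enrolment of 280. The plan never states 280.
- 480 × 0.70 = 336, not 287. But the 480 counts participants and the acceptance rate is given for patients, so 336 is not a figure to which the plan commits.
- The enrolment period is three years in section 5 and 2.5 years in section 9. This is a timeline discrepancy and has no bearing on 238.

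Nor should 219 be read as a rival final sample, given the likely origin of 141.

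**Conclusion.** The inconsistency is established by arithmetic on the plan's own numbers: two incompatible rates in one sentence, two site rows that do not follow from their label, and site finals 19 short of the total. The possible final totals run from about 201 to 244 around the stated 238. The low end assumes that 70% retention was meant and that it applies to caregivers as well as patients, which section 5 does not say. Only then are both groups about 16% smaller than stated (37/238), with the illustrative detectable difference moving from 0.45 to 0.49 SD for patients and from 0.61 to 0.66 SD for caregivers. Under 15% there is essentially no change. No analysis method is affected. The figures need correcting because they are the plan's only statement of size and cannot all be true.

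**What to change.** 1. In section 5, state one 12-month retention rate and say whether it applies to caregivers as well as patients.
2. In section 8, recompute the total, site rows and patient/caregiver split so that they follow from that rate and add up:
   - At 15% attrition: 244 in total (NWH 82, FFCC 162), about 157 patients and 87 caregivers. Alternatively, keep 238 and call it a conservative target, with site finals that sum to it.
   - At 30% attrition: about 201 in total (NWH 68, FFCC 133), about 129 patients and 72 caregivers, with sections 2 and 4 restated to match.
3. As secondary tidying, show how 480 available leads to 287 enrolled, and align the enrolment period in sections 5 and 9.

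The cost is text and table edits. No extra recruitment or design change is needed, though the stated final sample becomes less favourable if 70% retention is the rate confirmed.
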